# 8.4 Withdrawal of individual subjects

Subjects can leave the study at any time for any reason if they wish to do so without any consequences. However, during informed consent, subjects will be informed that participation is not possible if they don't want to be informed about the results of the finger stick procedure or questionnaires. The investigator can decide to withdraw a subject from the study for urgent medical reasons.

# 8.4.1 Specific criteria for withdrawal (if applicable)

NA

# 8.5 Replacement of individual subjects after withdrawal

NA

8.6 Follow-up of subjects withdrawn from treatment

NA

### 8.7 Premature termination of the study

### 9. SAFETY REPORTING

### 9.1 Temporary halt for reasons of subject safety

In accordance to section 10, subsection 4, of the WMO, the sponsor will suspend the study if there is sufficient ground that continuation of the study will jeopardise subject health or safety. The sponsor will notify the accredited METC without undue delay of a temporary halt including the reason for such an action. The study will be suspended pending a further positive decision by the accredited METC. The investigator will take care that all subjects are kept informed.

### 9.2 AEs, SAEs and SUSARs

### 9.2.1 Adverse events (AEs)

Adverse events are defined as any undesirable experience occurring to a subject during the study, whether or not considered related to the finger stick procedure. All adverse events reported spontaneously by the subject or observed by the investigator or his staff will be recorded.

### 9.2.2 Serious adverse events (SAEs)

A serious adverse event is any untoward medical occurrence or effect that

- results in death;
- is life threatening (at the time of the event);
- requires hospitalisation or prolongation of existing inpatients' hospitalisation;
- results in persistent or significant disability or incapacity;
- is a congenital anomaly or birth defect; or
- any other important medical event that did not result in any of the outcomes listed above due to medical or surgical intervention but could have been based upon appropriate judgement by the investigator.

An elective hospital admission will not be considered as a serious adverse event.

The investigator will report all SAEs to the sponsor without undue delay after obtaining knowledge of the events, except for the following SAEs: NA

The sponsor will report the SAEs through the web portal *ToetsingOnline* to the accredited METC that approved the protocol, within 7 days of first knowledge for SAEs that result in death or are life threatening followed by a period of maximum of 8 days to complete the initial preliminary report. All other SAEs will be reported within a

period of maximum 15 days after the sponsor has first knowledge of the serious adverse events.

### 9.2.3 Suspected unexpected serious adverse reactions (SUSARs)

NA

Adverse reactions are all untoward and unintended responses to an investigational product related to any dose administered.

Unexpected adverse reactions are SUSARs if the following three conditions are met:

- 1. the event must be serious (see chapter 9.2.2);
- there must be a certain degree of probability that the event is a harmful and an undesirable reaction to the medicinal product under investigation, regardless of the administered dose;
- the adverse reaction must be unexpected, that is to say, the nature and severity of the adverse reaction are not in agreement with the product information as recorded in:
  - Summary of Product Characteristics (SPC) for an authorised medicinal product;
  - Investigator's Brochure for an unauthorised medicinal product.

The sponsor will report expedited the following SUSARs through the web portal *ToetsingOnline* to the METC:

- SUSARs that have arisen in the clinical trial that was assessed by the METC;
- SUSARs that have arisen in other clinical trials of the same sponsor and with the same medicinal product, and that could have consequences for the safety of the subjects involved in the clinical trial that was assessed by the METC.

The remaining SUSARs are recorded in an overview list (line-listing) that will be submitted once every half year to the METC. This line-listing provides an overview of all SUSARs from the study medicine, accompanied by a brief report highlighting the main points of concern.

The expedited reporting of SUSARs through the web portal Eudravigilance or ToetsingOnline is sufficient as notification to the competent authority.

The sponsor will report expedited all SUSARs to the competent authorities in other Member States, according to the requirements of the Member States.

The expedited reporting will occur not later than 15 days after the sponsor has first knowledge of the adverse reactions. For fatal or life threatening cases the term will be maximal 7 days for a preliminary report with another 8 days for completion of the report.

### 9.3 Annual safety report

### NA

In addition to the expedited reporting of SUSARs, the sponsor will submit, once a year throughout the clinical trial, a safety report to the accredited METC, competent authority, and competent authorities of the concerned Member States.

This safety report consists of:

- a list of all suspected (unexpected or expected) serious adverse reactions, along with an aggregated summary table of all reported serious adverse reactions, ordered by organ system, per study;
- a report concerning the safety of the subjects, consisting of a complete safety analysis and an evaluation of the balance between the efficacy and the harmfulness of the medicine under investigation.

# 9.4 Follow-up of adverse events

All AEs will be followed until they have abated, or until a stable situation has been reached. Depending on the event, follow up may require additional tests or medical procedures as indicated, and/or referral to the general physician or a medical specialist. SAEs need to be reported till end of study within the Netherlands, as defined in the protocol

# 9.5 [Data Safety Monitoring Board (DSMB) / Safety Committee]

# NA

The advice(s) of the DSMB will only be sent to the sponsor of the study. Should the sponsor decide not to fully implement the advice of the DSMB, the sponsor will send the advice to the reviewing METC, including a note to substantiate why (part of) the advice of the DSMB will not be followed.

### NL62337.029.17 / ParoSysACTA Periodontitis as signal for an underlying disease

### **10. STATISTICAL ANALYSIS**

The prevalence of (pre)DM and MetS, the 10-year risk of ASCVD and the risk of OSAS will be presented in tables. First, one table will be generated describing the background variables, blood chemistry and demographic characteristics. Secondly, the prevalence of (pre)DM and MetS, the 10-year-risk of CVD and the OSAS risk will be reported in patients with and without periodontitis.

According to the ADA guidelines HbA1c values will be classified as normal (<5.7% [<39 mmol/mol]), preDM (5.7-6.4% [39-47 mmol/mol]) and DM (≥6.5% [≥48 mmol/mol]) (7).

The 10-year risk of ASCVD will be assessed with help of the risk table from the Dutch guideline on cardiovascular risk management (CVRM) according to the standards of the Dutch College of General Practitioners (NHG) (20). The NHG standards are derived from European Society of Cardiology guidelines and modified to the Dutch situation (6).

According to the NCEP ATP III guidelines MetS is present if three of the 3 or more of the five criteria are met: elevated waist circumference over  $\geq$  102 cm (men) or  $\geq$  88 cm (women), triglyceride (TG) level over  $\geq$  1.7 mmol/L or being on drug treatment for elevated TG, high density lipoprotein cholesterol (HDL-C) level less than < 1.03 mmol/L (men) or < 1.3 mmol/L (women), blood pressure over 130/85 mmHg or on antihypertensive drug treatment, and blood glucose level over  $\geq$  5/6 mmol/L (21).

The OSAS risk is calculated with help of a new questionnaire (PhilipsQ) which is constructed from body measurements (sex, age, BMI, neck circumference) and the most predictive questions of the following OSAS and sleep questionnaires: Berlin Questionnaire (BerlinQ), STOP Questionnaire (STOPQ) and Athens Insomnia Scale (AIS). An algorithm is developed to compute the individual estimated probability (p) that a subject will have OSAS: p(OSAS) = 1 / (1+e-X), where  $X = -6.322 + 2.828 \times AIS + 2.745 \times STOPBANGQ$  High + 0.965 × STOPBANGQ Intermediate + 4.640 × BerlinQ High + 1.584 × BerlinQ Intermediate + 0.790 × Age + 0.810 × BerlinQ Q-5. The final cutoff values were determined by exploratory logistic regression analyzes. The risk of OSAS will be classified as low (p[OSAS] < 35%), intermediate (p[OSAS] = 35-55%) and high (p[OSAS] > 55%) (22).

The missing data from included subjects will be imputed using the expectationmaximization method. Background variables, blood chemistry and demographic data between cases and controls will be analysed by Chi-analyses or t-tests where applicable. The primary and secondary outcome variables will be analysed both by univariate analysis and multivariate analysis (multiple logistic regression). The data will be analysed on an intention-to-treat basis (ITT).

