**Study population:** In total 783 patients will be included (261 without periodontitis, 261 with mild/moderate periodontitis and 261 with severe periodontitis) at the Academic Centre for Dentistry Amsterdam (ACTA). The subjects with periodontitis that will be enrolled in this study are referred to the periodontal clinic for diagnosis and treatment of periodontitis. The subjects without periodontitis will be selected among individuals that visit the dental school for regular dental checkups. All subjects will be 18 years and older and are mainly inhabitants from Amsterdam and surrounding areas.

**Intervention (if applicable)**: Subjects with and without periodontitis will undergo the following intervention:

- General, medical and dental histories (standard procedure)
- Clinical periodontal evaluation (standard procedure)
- Dental x-rays, when indicated for periodontitis or other dental pathology (standard procedure)
- Measurement of systolic and diastolic blood pressure (standard procedure)
- Measurement of length and body weight, waist and neck circumference, a questionnaire for demographic characteristics, an International Physical Activity Questionnaire (IPAQ) and an OSAS risk questionnaire (extra procedure)
- Plasma finger stick procedure (HemCol, Labonovum BV) for measuring biomarkers: A drop of blood is obtained with a finger stick (Greiner Bio-one Safety Lancet) and collected in a collection tube. The collection tube is sent to the laboratory for analysis by regular mail. (extra procedure)

**Main study parameters/endpoints:** To investigate, within a dental setting, the differences between subjects with and without periodontitis in:

- The prevalence of preDM and DM
- The 10-year-risk of ASCVD
- The prevalence of MetS
- The risk of OSAS

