### Hypothesis

- We put the hypothesis forward that periodontitis patients show an increased prevalence of (pre)DM, an increased 10-year-risk of ASCVD, an increased prevalence of MetS and an increased risk of OSAS compared with subjects without periodontitis.

Notably, a recently published pilot paper from our group presented the feasibility and preliminary results of proposed screening for (pre)DM; we found 18.1% new DM cases among subjects with severe periodontitis compared to 9.9% in mild/moderate periodontitis and 8.5% in controls (13).

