### 4.4 Sample size calculation

The calculation of the sample size was based on a  $Chi^2$ -test having an  $\alpha$ <0.05 with 90% power and using the prevalence of diabetes of two groups (without periodontitis: 8.5%, severe periodontitis: 18.1%)(13). The required sample size is a minimum of 261 subjects per group.

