### **10.1 Primary study parameter(s)**

The cases and controls are a priori defined by inclusion and exclusion criteria. The STROBE guideline will be followed and a flow diagram will be generated of how many individuals have been screened, invited to participate, included and analysed (29). All initially included study subjects will form part of the data analysis (intention to treat). Type I error will be controlled by including a sufficient number of cases and controls to avoid multiplicities and to apply Bonferroni corrections where applicable. Secondly, we have determined the minimal sample size on the basis of an appropriate power calculation (see chapter 4.4).

The prevalence of (pre)diabetes, the 10-year risk of ASCVD, the prevalence of MetS and the prevalences of OSAS risks (categorical variables) within the study population will be compared with parametric and non-parametric tests (ANOVA and  $Chi^2$ -test). Where applicable, analyses will be corrected for multiple testing (Bonferroni). The significance level will be set to p<0.05.

The prevalence of (pre)DM among cases and controls will be firstly reported without adjustment of any of potential covariates. In a second exploratory analysis we will adjust the prevalence for general and diabetes and ASCVD related characteristics of the study population: sex, age, ethnicity (origin of parents), education level, smoking habits, relatives with DM, history of periodontal treatment, diagnosis of hypertension, diagnosis of hypercholesterolemia, diagnosis of DM and the BMI, amount of physical activity.

The 10-year risk of ASCVD will be calculated according to the algorithm from the ESC guidelines, which is adapted to the Dutch situation. No further adjustments will be done.

The prevalence MetS will be calculated according to the criteria of the NCEP ATP III guidelines. No covariates will be included.

The risk for OSAS will be assessed by the OSAS questionnaire. No further adjustments will be done. However, the results will be explored in relation to having periodontitis, the

background characteristics, the blood chemistry outcomes and having (pre)diabetes and the 10-year risk for ASCVD.

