### 10.2 Secondary study parameter(s)

The secondary research aim is to investigate whether there are differences between severe periodontitis and mild/moderate periodontitis. As such, mild/moderate periodontitis will be labelled as "control" while severe periodontitis patients are labelled as "cases". In secondary analyses exact procedures are followed as described above for the primary outcomes.

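### Three ordered severity groups are recruited, but the primary comparison pools two of them and no ordered test is planned; at the pilot diabetes rates the pooled test has about 62% power, not 90%

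*Combined protocol and SAP*

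**What the plan says.** The Summary plans three groups: "261 without periodontitis, 261 with mild/moderate periodontitis and 261 with severe periodontitis". Appendix 5 supplies a graded case definition from none to severe. The Hypothesis section reports a pilot with "18.1% new DM cases among subjects with severe periodontitis compared to 9.9% in mild/moderate periodontitis and 8.5% in controls".

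The comparisons are described in two-group terms. The objectives (section 2) and the main endpoint (section 8.1.1) set subjects with periodontitis against those without. Section 10 describes the results table the same way: "Secondly, the prevalence of (pre)DM and MetS, the 10-year-risk of CVD and the OSAS risk will be reported in patients with and without periodontitis". Section 10.1 uses case/control language: "The prevalence of (pre)DM among cases and controls will be firstly reported without adjustment of any of potential covariates". Section 10.2 turns to the secondary aim: "As such, mild/moderate periodontitis will be labelled as" the control group, severe patients become the cases, and the primary procedures are repeated.

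The tests named are ANOVA, Chi2 and multiple logistic regression. Section 10.1 does not say whether the Chi2 test has two groups or three. No trend test or ordered coding of severity appears. The sample size in section 4.4 rests on another contrast, "using the prevalence of diabetes of two groups (without periodontitis: 8.5%, severe periodontitis: 18.1"%.

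**The concern.** The rationale is that periodontitis may signal underlying disease, and the pilot places almost all of the diabetes signal in severe disease: mild/moderate patients are 1.4 points above controls (9.9% against 8.5%), severe patients 9.6 points above. Pooling the two severities averages a clear difference with almost none. The secondary contrast then leaves out the 261 controls. If the pilot is right, the primary comparison could well be non-significant in a study whose stated power is 90%. A reader of section 4.4 would take that 90% to apply to the primary comparison.

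**Working it through.** **Inputs.** 261 per group (Summary, section 4.4). DM rates 8.5%, 9.9% and 18.1% (Hypothesis). Level: "The significance level will be set to p<0.05" (section 10.1). Section 4.4 plans for "<0.05 with 90% power". Assumptions: two-sided testing (sidedness is not stated), Chi2 without continuity correction, trend scores 0, 1, 2.

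**Step 1: the plan's own figure.** For none versus severe, with p̄ = (0.085 + 0.181)/2 = 0.133:

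n = [1.960·√(2p̄(1−p̄)) + 1.2816·√(p1(1−p1) + p2(1−p2))]² / (p2−p1)²
= [1.960·√0.23062 + 1.2816·√0.22601]² / 0.096² = 2.404/0.009216 = 260.9, so 261.

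The stated 261 is reproduced, which supports the two-sided reading.

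**Step 2: with versus without.** Pooled periodontitis rate (9.9 + 18.1)/2 = 14.0%, so 8.5% (n = 261) against 14.0% (n = 522). Power = Φ[(d − 1.960·SE0)/SE1], where SE0 uses the common rate and SE1 the separate rates. With d = 0.055, SE0 = 0.02478 and SE1 = 0.02299:

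(0.055 − 0.04857)/0.02299 = 0.280, so power is 61.0%.

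**Step 3: severe versus mild/moderate.** d = 0.082, SE0 = 0.03037, SE1 = 0.03016: (0.082 − 0.05953)/0.03016 = 0.745, so power is 77.2%.

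**Step 4: trend.** With equal groups and scores 0, 1, 2, the Cochran-Armitage numerator reduces to severe minus none. The mild/moderate group enters only through the overall rate, (8.5 + 9.9 + 18.1)/3 = 12.17%. With d = 0.096, SE0 = √(0.1217·0.8783·2/261) = 0.02862 and SE1 = 0.02943: (0.096 − 0.05609)/0.02943 = 1.356, so power is 91.3%.

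**Step 5: three-group Chi2, 2 df.** Noncentrality 261·Σ(p − p̄)²/[p̄(1−p̄)] = 13.14, giving 91.1%.

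**Step 6: simulation (200,000 trials).**

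| Test, pilot rates | Formula, 0.05 | Simulated, 0.05 | Simulated, 0.0125 |
|---|---|---|---|
| With v without | 61.0% | 61.9% | 38.8% |
| Severe v mild/moderate | 77.2% | 78.0% | 58.5% |
| Three-group Chi2 | 91.1% | 89.7% | 77.8% |
| Trend | 91.3% | 91.6% | 80.4% |
| None v severe (section 4.4) | 90.0% | 90.7% | 77.9% |

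The 0.0125 column assumes Bonferroni over four main outcomes; the plan gives no divisor.

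**Step 7: where the loss arises.** From pooled to three-group Chi2: 89.7 − 61.9 = 27.8 points. From three-group Chi2 to trend: 91.6 − 89.7 = 1.9 points. Pooling accounts for nearly all of it.

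**Step 8: other patterns (assumed rates, simulated, 0.05).**

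| None / mild-moderate / severe | With v without | Three-group Chi2 | Trend |
|---|---|---|---|
| 8.5 / 13.3 / 18.1% (halfway) | 82.9% | 84.3% | 90.5% |
| 8.5 / 14 / 14% (one rate) | 61.8% | not needed | 48.4% |
| 8.5 / 16 / 16% (one rate) | 85.4% | not needed | 71.9% |

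With a halfway middle rate, ignoring order costs 90.5 − 84.3 = 6.2 points. With one shared rate the trend is 13.4 to 13.5 points weaker than the pooled test.

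**The case against.** A reader might infer that the roughly 30-point gap between the pooled test and the trend is the price of having no trend test. Step 7 does not support that: an unordered three-group test recovers most of it.

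A reader might also take it as settled that the plan tests only two yes/no splits. Section 10.1 leaves the number of groups open, and naming ANOVA there, where section 10 uses t-tests for the case/control background comparisons, fits a three-group test. On that reading the loss at the pilot rates is about 2 points. The objectives, the results table and the relabelling in section 10.2 favour two groups, but the text does not decide it.

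It is also fair that the trend test is close to section 4.4's none-versus-severe contrast, since the middle group has zero weight in the numerator. Its power should not be credited to making full use of 783 subjects.

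The strongest objection is to replacing the primary test. The hypothesis and primary objective concern periodontitis against none, and severity is a declared secondary aim. A trend test can reject when only severe disease differs, and it loses power if both severities share one rate. This stands: the documents do not support replacing the with/without comparison.

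Finally, the two planned contrasts together are stronger than either alone. In simulation at least one rejects in 90.7% of trials at 0.05 each, though in 83.1% at 0.025 each. That softens the consequence for the study as a whole but does not raise the power of the primary comparison.

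**Conclusion.** The concern holds in limited form. The plan recruits three ordered groups, describes two-group comparisons, names no ordered test and leaves the number of groups in its Chi2 test unstated. If the primary test is with versus without, its power for DM at the pilot rates is about 62%, some 28 points below the 90% in section 4.4. A prespecified severity trend has about 92% at the same sample size. Pooling is the main cause, and the benefit of using order is about 2 points at the pilot rates and about 6 if the middle rate is halfway.

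This rests on two-sided 0.05 without multiplicity adjustment, equal groups, and the pilot's rates of new DM. The endpoint also includes preDM, and section 4.3 has no exclusions, so known diabetes enters too. The documents give no severity-specific rates for preDM, MetS, ASCVD risk or OSAS, so no gain can be claimed for those outcomes.

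**What to change.** In section 10.1:

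- State how many groups the Chi2 test compares.
- Prespecify, for DM and MetS, a Cochran-Armitage trend test across none, mild/moderate and severe (scores 0, 1, 2), and enter severity as an ordered term in the logistic model where one is fitted.
- Count the trend test in the Bonferroni correction, and give the divisor.
- Keep with versus without, as the stated primary objective, and severe versus mild/moderate, each as a contrast with a confidence interval.

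In section 10, show all three group prevalences in the results table. In section 4.4, state that the 90% applies at unadjusted 0.05 to none versus severe (or the trend), not to the pooled comparison.

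This needs no new subjects, data or procedures, but the change goes to the ethics committee under section 12.3. The statistical cost is one further test for each of the two outcomes in the correction. The trend also has about 13 points less power than the pooled contrast if the two severities share one rate, which is not what the pilot shows.

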# 2. OBJECTIVES

Primary Objective:

To investigate, within a dental setting, the differences between subjects with and without periodontitis in:

- The prevalence of preDM and DM (established cut-off values for HbA1c, appendix 1 and 2 (7))
- The 10-year-risk of ASCVD ("10-year-risk" chart, appendix 3 (20))
- The prevalence of MetS (diagnostic criteria of NCEP ATP III, appendix 4 (21))
- The risk of OSAS (OSAS risk questionnaire (22))

Secondary Objective(s):

- To investigate the differences in (pre)DM prevalence, 10-year-risk of ASCVD, MetS prevalence and OSAS risk between mild/moderate and severe periodontitis patients

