All subjects will receive two letters with the result of the plasma finger stick procedure, on which the values of HbA1c, total cholesterol, LDL-C, HDL-C, triglycerides, CRP, creatinine will be reported. One letter is for the subject and the other letter is for their general practitioner (GP). The patient can decide to bring this letter to their GP. All subjects will be orally informed about their systolic and diastolic blood pressure by their dentist or researcher. When the blood values are above the known cut-off values and/or the 10-year risk of ASCVD is increased and/or the risk of OSAS is high, then the patient will be advised to visit the general practitioner for further diagnosis. An information brochure from the Thuisarts.nl, developed by the NHG, will be given when a high risk of cardiovascular diseases is suspected. Another information brochure from the The Sleep Apnea about sleep apnea will be given when the risk of OSAS is increased.

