### **10.3 Other study parameters**

Other study parameters that will be obtained and used as covariates are sex (M/F), age (years), ethnicity (origin of parents) (Europe/Non-Europe), education level (high/low), smoking habits (yes/no), diagnosis of hypertension (yes/no), diagnosis of ASCVD (yes/no), medical treatment for ASCVD (yes/no), relatives with ASCVD (yes/no), diagnosis of hypercholesterolemia (yes/no), medical treatment for hypercholesterolemia (yes/no), diagnosis of DM (yes/no), relatives with DM (yes/no), history of periodontal treatment (yes/no), height (cm) and body weight (kg) (for determining the BMI), neck and waist circumference (cm), blood pressure (mmHg), physical activity (Metabolic Equivalent of Task).

**10.4 Interim analysis (if applicable)** NA

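### The OSAS risk formula in section 10 does not say how Age or AIS is coded, and with age in years, the only unit the plan gives, every eligible adult is classed as high risk

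*Combined protocol and SAP*

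**What the plan says.** Sections 2 and 8.1.1 list OSAS risk among the four primary comparisons: "The risk of OSAS (OSAS risk questionnaire (22". Section 10.1 analyses it as a categorical variable without further adjustment, and section 10.2 repeats the comparison for severe against mild/moderate periodontitis.

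Section 10 prints the scoring rule in full. It is a logistic probability with intercept −6.322, a term of 2.828 for AIS, a term of 2.745 for the high STOPBANG level, then "0.965 × STOPBANGQ Intermediate + 4.640 × BerlinQ High + 1.584 × BerlinQ Intermediate", and finally "0.790 × Age + 0.810 × BerlinQ Q-5". The result is "classified as low (p[OSAS] < 35%), intermediate (p[OSAS] = 35-55%) and high (p[OSAS] > 55"%.

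The STOPBANG and Berlin terms carry level labels, so they can be read as indicators. Age, AIS and BerlinQ Q-5 carry no label, unit or cut-off. Section 10.3 gives the recorded form of age: "used as covariates are sex (M/F), age (years". Section 4.2 sets the minimum age at 18 years.

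The class also has a use outside the analysis. Section 8.3 says that if "the risk of OSAS is high, then the patient will be advised to visit the general practitioner for further diagnosis".

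**The concern.** A scoring rule printed with its coefficients invites direct programming. An analyst who applies it to the age variable that the plan records would multiply 0.790 by at least 18 and swamp the intercept. The OSAS class would then be the same for every subject, and neither the primary nor the secondary OSAS comparison could show anything. The same class prompts advice to participants, so a coding error would reach them as well as the tables.

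**Working it through.** **The plan's own figure.** The plan gives no worked OSAS probability to reproduce. Its one calculated figure is the 261 per group in section 4.4. A two-sided chi-square test with pooled variance and no continuity correction, for 8.5% against 18.1%, gives

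n = [1.960·√(2 × 0.133 × 0.867) + 1.282·√(0.085 × 0.915 + 0.181 × 0.819)]² / 0.096² ≈ 261.

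The figure is reproduced. It rests on diabetes prevalence and does not involve the OSAS formula.

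**Inputs.** From section 10: the coefficients, p = 1/(1 + e^(−X)), and the limits 35% and 55%. From 10.3: age in years. From 4.2: minimum age 18. Assumption: the other terms are coded zero or positive.

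**Age in years, all other terms at zero.**

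- Age 18: X = −6.322 + 0.790 × 18 = 7.898, so p = 99.963%.
- Age 25: X = −6.322 + 0.790 × 25 = 13.428, so p = 99.9999%.
- Age 40: X = 25.278, so p differs from 1 by about 1 in 10¹¹.

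All other printed coefficients are positive, so 99.963% is the minimum for an eligible adult. The class limits on the X scale are ln(0.35/0.65) = −0.619 and ln(0.55/0.45) = 0.201. They are crossed at ages (−0.619 + 6.322)/0.790 = 7.2 years and (0.201 + 6.322)/0.790 = 8.3 years, both far below 18.

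**Other codings of Age.** I took all 36 combinations of the other terms: AIS 0/1, three STOPBANG levels, three Berlin levels, Q-5 0/1. The 0/1 coding of AIS and Q-5 is an assumption. The counts are numbers of possible profiles, not expected proportions of participants.

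| Assumed value of Age | Lowest p | Low / intermediate / high |
|---|---|---|
| Years, 18 | 99.963% | 0 / 0 / 36 |
| Years, 50 | about 100% | 0 / 0 / 36 |
| Indicator 0 | 0.18% | 23 / 3 / 10 |
| Indicator 1 (or first ordinal band) | 0.39% | 17 / 6 / 13 |
| Third ordinal band (3) | 1.9% | 9 / 4 / 23 |
| Decades, 1.8 (age 18) | 0.74% | 13 / 4 / 19 |
| Decades, 4 (age 40), or fourth ordinal band | 4.1% | 6 / 4 / 26 |
| Decades, 5 (age 50) | 8.5% | 4 / 3 / 29 |
| Decades, 7 (age 70) | 31.2% | 1 / 2 / 33 |
| Decades, 8 (age 80) | 49.95% | 0 / 1 / 35 |

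Indicator, ordinal and decade codings all separate subjects, but differently. A 50-year-old could have Age = 1 under an indicator and Age = 5 under decades. Between those two values X shifts by 4 × 0.790 = 3.16. Of the 17 low profiles, 4 stay low and 13 move up. All 6 intermediate profiles become high, because the shift exceeds the width of the intermediate band (0.201 + 0.619 = 0.820). So 19 of 36 profiles change class.

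**AIS.** Section 10 calls it a scale but gives no coding. Entered as a numeric score, a value of 3 with everything else at zero, Age included, gives X = −6.322 + 2.828 × 3 = 2.162 and p = 89.7%, which is in the high class.

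**The case against.** The unit of years stands in a covariate list in 10.3, not in the definition of the score. Section 10 gives no unit, and the endpoint is defined by citing reference 22, which may settle the coding. The context also argues against years. STOPBANG and Berlin enter as levels, three classes cut at 35% and 55% would be pointless if everyone scored near 100%, and the ASCVD chart in Appendix 3 shows that a score can enter age by band. A coefficient of 0.790 multiplies the odds by e^0.790 = 2.2 per unit, or by e^7.9 ≈ 2,700 over ten years if the unit is one year. The printed formula shows damage from text extraction, so a lost qualifier on Age cannot be ruled out. A score of nearly 100% for everyone would also be noticed early, and the scores could be recalculated.

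Much of this stands. A reader might infer that the OSAS endpoint is bound to be constant, with 783 of 783 at high risk. The documents do not support that, because the loss of contrast is conditional on entering age in years. Nor do they support the inference that Age must be an indicator or category: a decade coding also separates subjects. A reader might also see a contradiction between the STOP questionnaire named as a source and the STOPBANG levels in the formula. None is shown, since section 10 lists sex, age, BMI and neck circumference among the inputs as well.

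The objection does not make the printed rule usable. Concluding that age is probably coded in some other way does not tell the analyst which way, and the table shows that the class depends on it.

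**Conclusion.** The concern holds in conditional form. As printed, the OSAS formula cannot be applied from the plan. In the plan's only stated unit for age, every eligible adult has p of at least 99.96% and is classed as high risk, given non-negative coding of the other terms. Under any other coding the classes can separate, but the documents do not say which coding applies, so no subject's class can be reproduced. AIS has the same gap, and BerlinQ Q-5 is also uncoded. This is an undefined input to a primary comparison, not a miscalculated figure in the plan. It should be corrected before scoring begins, because the class also feeds the advice in 8.3. The diabetes, ASCVD and MetS comparisons and the sample size do not depend on it.

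**What to change.** In section 10, replace Age and AIS in the formula with the coded terms and cut-offs that reference 22 uses, whatever they are, and state the coding of BerlinQ Q-5. Before any participant is classified, run the scoring program on a few invented subjects, from a symptom-free young adult to one with every item positive. Confirm that low, intermediate and high can all occur, and put one worked example in the plan.

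The cost is one corrected formula line, a short coding note and a scoring check. Age is already recorded in years, so any banding can be derived from it. Data collection and the 261 per group do not change.
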